## List of Figures

## Protocol Summary

**Study Compound:** BOTOX® (Botulinum Toxin Type A) Purified Neurotoxin Complex (US Adopted Name is OnabotulinumtoxinA)

**Phase:** 3

**Study Objective:** To evaluate the safety and efficacy of BOTOX for the treatment of urinary incontinence due to neurogenic detrusor overactivity (NDO) in patients 5 to 17 years of age who have not been adequately managed with anticholinergic therapy

**Clinical Hypotheses:** BOTOX (one or more of the treatment groups) has an acceptable safety profile when injected into the detrusor of patients 5 to 17 years of age with NDO. BOTOX (one or more of the treatment groups) improves the symptoms of NDO as measured by a reduction from baseline in daytime urinary incontinence episodes.

### Study Design

*Structure:* Multicenter, randomized, double-blind, parallel group

*Duration:* Patients will participate in the study until one of the following exit criteria is met, whichever occurs sooner:

- patient has qualified for retreatment (retreatment to occur in the extension study, for patients who elect and qualify to enroll), or
- patient has completed 48 weeks after randomization/day 1, if never qualifies for retreatment (ie, completes the 48 week visit)

*Study Treatment Groups:* There will be 3 treatment groups:

- 50 U BOTOX (not to exceed 6 U/kg)
- 100 U BOTOX (not to exceed 6 U/kg)
- 200 U BOTOX (not to exceed 6 U/kg)

*Controls:* None

*Dosage/Dose Regimen:* A single treatment will be administered on day 1 once all “day of treatment criteria” are fulfilled (see Section 5.9.1). Treatment will be administered via cystoscopy (rigid or flexible cystoscope) as 20 intradetrusor injections of 0.5 mL each evenly distributed, sparing the trigone. Administration will be under general anesthesia (see Section 5.9.3 for details) for all patients < 12 years of age. For patients 12 years and older, administration can be under local anesthesia (with or without sedation), or general anesthesia.

Precautions for latex sensitivity or allergy will be taken, in accordance with local site practice.

Qualification for retreatment can occur in this study (see Section 5.10); however, the patient will exit this study once qualified for retreatment and treatment administration will occur in the extension study (patients who never qualify for retreatment can also enroll into the extension study once they complete this study [ie, 48 weeks from randomization/day 1]).

*Randomization/Stratification:* Patients will be randomized on day 1 to one of 3 treatment groups:

- 50 U BOTOX (not to exceed 6 U/kg)
- 100 U BOTOX (not to exceed 6 U/kg)
- 200 U BOTOX (not to exceed 6 U/kg)

Patients will be centrally randomized and assigned a randomization number prior to treatment. In order to ensure balance across treatment groups, patients will be stratified by age (< 12 years or ≥ 12 years), and baseline daytime urinary incontinence episodes (a total of ≤ 6 episodes or > 6 episodes over the 2-day diary collection period).

## Study Population Characteristics

*Number of Patients:* Approximately 132 patients will be randomized at approximately 35 to 45 sites (40 patients per treatment group plus 10% dropout by the primary timepoint of week 6).

*Condition/Disease:* Urinary incontinence due to NDO

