**Sample Size Calculation:** The sample size calculation for this study is determined empirically. A total of 34 patients per treatment group are to be randomized for the study (30 patients per treatment group plus additional patients to address patient attrition [estimated to be 10% by week 6]).

[figure not shown]
The following table displays the estimated distance for treatment differences between 200 U BOTOX (maximum 6 U/kg) and 50 U BOTOX (maximum 6 U/kg) in mean daily average frequency of daytime episodes of urinary incontinence change from baseline at week 6 for a range of common standard deviations (SD). All calculations assume 30 patients per treatment group and a 2-sided test significance level of 0.05. The calculation was performed using the commercial software nQuery Advisor (procedure MTC0-1), version 6.01, and the confidence interval is based on the large sample z statistic.

Standard Deviation	Distance From Mean to the Limit
2.0	1.012
2.5	1.265
3.0	1.518
3.5	1.771
4.0	2.024

Note: The ranges of the SDs are determined based on the values from the adult pivotal phase 3 studies (191622-515 and 191622-516). The estimate of the SD for the 200 U BOTOX treatment group is 3.44 for Study 191622-515, 2.58 for Study 191622-516, and 3.10 for the 2 studies combined.

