## **4 Study Population and Entry Criteria**

### **4.1 Number of Patients**

Approximately 102 patients will be randomized at approximately 35 to 45 sites in order to have an estimated 90 patients (30 per treatment group) based on an anticipated dropout rate of 10% by the primary timepoint of week 6.

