## 7.7 Sample Size Calculation

The sample size calculation for this study is determined empirically, while taking into account the treatment effect observed in the adult pivotal phase 3 studies, 191622-515 and 191622-516. The mean (standard deviation) of the change from baseline in daily urinary incontinence at week 6 was -3.1 (3.44) and -3.1 (2.58) in Studies 191622-515 and 191622-516, respectively.

Approximately 34 patients per treatment group are to be enrolled for the study. This includes 30 patients per treatment group and an increase to 34 per group in order to address patient attrition (estimated to be 10% by week 6)

The following table displays estimates of the distance for treatment differences between BOTOX 200 U (maximum 6 U/kg) and 50 U (maximum 6 U/kg) in mean daily average frequency of daytime episodes of urinary incontinence change from baseline at week 6 for a range of common standard deviations (SD). All calculations assume 30 patients per treatment group and a 2-sided test significance level of 0.05. The calculation was performed using the commercial software nQuery Advisor (procedure MTC0-1), version 6.01, and the CI is based on the large sample z statistic.

Standard Deviation	Distance From Mean to the Limit
2.0	1.012
2.5	1.265
3.0	1.518
3.5	1.771
4.0	2.024

Note: The ranges of the SDs are determined based on the values from the adult pivotal phase 3 studies (191622-515 and 191622-516). The estimate of the SD for the 200 U BOTOX treatment group is 3.44 for Study 191622-515, 2.58 for Study 191622-516, and 3.10 for the 2 studies combined.

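### The Protocol Summary still gives an enrolment target of 132 (40 per group), while its own sample-size paragraph and Sections 4.1 and 7.7 give 34 per group, or 102 (30 per group after attrition)

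*Protocol*

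**What the plan says.** The protocol states the enrolment target in four places.

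- **Protocol Summary, Number of Patients:** "Approximately 132 patients will be randomized at approximately 35 to 45 sites (40 patients per treatment group plus 10% dropout" by the week 6 timepoint).
- **Protocol Summary, Sample Size Calculation:** "A total of 34 patients per treatment group are to be randomized for the study", made up of 30 per group plus an allowance for 10% attrition by week 6.
- **Section 4.1:** "Approximately 102 patients will be randomized at approximately 35 to 45 sites in order to have an estimated 90 patients (30 per treatment group"). The dropout allowance here is likewise 10% at week 6.
- **Section 7.7:** "Approximately 34 patients per treatment group are to be enrolled for the study", again 30 per group raised to 34 for attrition.

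Sections 3 and 5.4 specify three groups in a 1:1:1 ratio. The precision table appears in both the Summary and Section 7.7. In Section 7.7 its basis is stated as "All calculations assume 30 patients per treatment group and a 2-sided test significance level of 0.05", and "the CI is based on the large sample z statistic". SAP Section 1.3 gives no number and refers the reader to protocol Section 7.7.

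**The concern.** The first statement cannot stand beside the other three. They share the same range of sites (35 to 45, in the two places that give it), the same 10% dropout and the same week 6 timepoint, yet one leads to 132 patients and the others to 102. The word approximately does not cover a gap of 30.

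This matters for two reasons. First, the number of children to be enrolled is a basic figure of the trial. Treatment is cystoscopic injection, under general anaesthesia for every patient under 12, so the number exposed should be stated once and consistently, including in a summary that may be read on its own. Second, the sample size is described as empirical and is supported only by the width of a confidence interval. The number per group is therefore the whole justification, and the published interval widths belong to one of the two targets only.

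**Working it through.** **Inputs.** Three groups, 1:1:1 (Sections 3 and 5.4). Dropout 10% by week 6 (Section 4.1). 30 per group, two-sided 0.05, large-sample z (Section 7.7). SD 2.0 to 4.0, with adult 200 U estimates of 3.44, 2.58 and 3.10 combined (Section 7.7). 40 per group (Protocol Summary, Number of Patients).

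**Step 1: the target of 102.** Divide by the expected retention: 30 / (1 − 0.10) = 33.3, rounded up to 34. Then 34 × 3 = 102. In the other direction, 102 × 0.90 = 91.8, or 30.6 per group, which agrees with the roughly 90 patients in Section 4.1.

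**Step 2: the target of 132.** Adding 10% gives 40 × 1.10 = 44, and 44 × 3 = 132. Dividing by retention would give 40 / 0.90 = 44.4, rounded up to 45, and 45 × 3 = 135. The figure of 132 therefore follows from adding 10%, whereas 102 follows from dividing by 0.90 (adding 10% to 30 would give 33 per group, or 99). In the other direction, 132 × 0.90 / 3 = 39.6 per group. The 132 is coherent with its own 40 per group, so it is a different target and not a misprinted digit.

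**Step 3: the precision table.** The half-width for a difference of two means with a common SD is 1.96 × SD × √(2/n), with n per group.

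| SD | Protocol table | Recomputed, n = 30 | Recomputed, n = 40 |
|---|---|---|---|
| 2.0 | 1.012 | 1.012 | 0.877 |
| 2.5 | 1.265 | 1.265 | 1.096 |
| 3.0 | 1.518 | 1.518 | 1.315 |
| 3.5 | 1.771 | 1.771 | 1.534 |
| 4.0 | 2.024 | 2.024 | 1.753 |
| 3.10 (adult, combined) | not tabulated | 1.569 | 1.359 |

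All five published values reproduce at n = 30. None belongs to n = 40. The n = 40 column is calculated here and appears nowhere in the protocol.

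**Step 4: size of the difference.** Randomised: 132 − 102 = 30, and 30 / 102 = 29%. After attrition: 40 − 30 = 10 per group. Half-width ratio: √(40/30) = 1.155, so the interval at 30 per group is 15.5% wider at any SD.

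**Step 5: sensitivity to the number analysed.** The primary analysis uses the mITT population with last observation carried forward to week 6, so the number analysed may exceed the post-attrition figure. If every randomised patient were analysed, the half-widths at SD 3.0 would be 1.426 (n = 34) and 1.254 (n = 44), a ratio of 1.14. The gap in precision is about the same.

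**The case against.** The strongest reply is that this is one line left behind by an amendment. The Amendment 3 summary records a reduction from 132 to 102 and lists the synopsis among the changed sections, so the intended figure is hardly in doubt. The SAP points to Section 7.7, which is correct, so no model, hypothesis, population or multiplicity rule takes up the wrong number. The Summary also prints 34 per group and the n = 30 table itself, so its reader meets an inconsistency and is never shown a narrower interval. The figure 102 is printed as the current target only in Section 4.1; elsewhere it has to be inferred from 34 per group. Finally, the documents do not show that the Number of Patients entry drives supply or randomisation, which run through a central system.

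Most of this stands. The defect is one of consistency, the sample-size derivation is correct, and the precision at 40 per group is an inference by the reader. It does not remove the conflict, which lies entirely within current text and does not need the amendment summary to establish it. The amendment summary helps only in showing which figure is meant. A reader of the Summary still finds two targets 30 children apart, with nothing there to say which one governs.

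**Conclusion.** The concern holds. The protocol carries two live enrolment targets: 132 randomised with 40 per group after attrition, and 102 randomised with 30 per group. The difference is 30 children, 29% of the smaller target. The published precision belongs to the smaller one: 1.518 at SD 3.0, against 1.315 had 40 per group been meant, and 1.569 against 1.359 at the combined adult SD of 3.10. These half-widths assume equal groups, a common SD and the z-based interval that the protocol uses, and the SDs come from adults. The 15.5% ratio needs the first three assumptions but does not depend on the value of the SD. The point should be corrected because the sample size is a figure that the trial relies on, but it does not affect the validity of the planned analysis.

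**What to change.** In the Protocol Summary, replace the Number of Patients entry with approximately 102 randomised: 34 per group, allowing for 30 per group after an estimated 10% attrition by week 6. That agrees with the Summary's sample-size paragraph, Sections 4.1 and 7.7, and the precision table. It also removes the difference in how dropout is allowed for, since 132 adds 10% while 102 divides by 0.90. It would help to print the total of 102 in Section 7.7 and in the Summary's sample-size paragraph, where only the number per group now appears.

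The cost is a one-line protocol correction. No patients are added and no analysis, table or SAP text has to change. The size stated in the Summary becomes smaller, and the precision it implies lower, but both then agree with the rest of the protocol.

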### *Key Inclusion Criteria:*

- patient must be regularly using clean intermittent catheterization (CIC) to empty the bladder

*Key Exclusion Criteria:*

- patient has had surgery of the spinal cord within 6 months of screening

- patient has cerebral palsy

- patient currently uses or plans to use a baclofen pump
- patient currently uses or plans to use an implantable or nonimplantable electrostimulation/neuromodulation device for treatment of NDO. (If a nonimplantable device is used, it must be discontinued at least 7 days prior to the first screening procedure; if a device is implanted, it must be inactive for at least 4 weeks prior to the first screening procedure; neither should be used during the study).
- patient uses an indwelling catheter, rather than CIC, for treatment of NDO (NOTE: an indwelling catheter can be used if needed overnight, as long as it is not used during the diary collection periods)
- patient has had previous or current:
  - botulinum toxin therapy of any serotype for any urological condition, or
  - treatment with botulinum toxin of any serotype within 3 months of randomization/day 1 for any other condition or use

### Response Measures

#### *Efficacy:*

##### Primary:

- daytime urinary incontinence episodes

[figure not shown]
##### Secondary:

- maximum cystometric capacity (MCC)
- presence/absence of an IDC
- if an IDC is present, maximum detrusor pressure during the first IDC ( $P_{det,Max1stIDC}$ )
- maximum detrusor pressure during the storage phase ( $P_{det,Max}$ )
- if a leak occurs, detrusor leak point pressure (DLPP)
- urine volume of first morning catheterization
- presence/absence of night time urinary incontinence
- time to patient request and time to qualification for retreatment

#### *Safety:*

- adverse events
- serious adverse events

**General Statistical Methods and Types of Analyses:** For efficacy variables, data will be analyzed using the modified intent-to-treat (mITT) population consisting of all randomized patients who receive treatment on randomization/day 1. Patients will be analyzed using their randomized treatment assignment except for those patients who triggered the 6 U/kg limit who will be grouped according to the nearest dose group (50, 100, or 200 U BOTOX) based on the dose actually received. The primary efficacy variable is the change from baseline at week 6 posttreatment in the daily average frequency of daytime urinary incontinence episodes, with baseline frequency defined as the daily average frequency of daytime urinary incontinence episodes preceding the study treatment.

For each of the BOTOX doses, descriptive statistics will be provided for the daily average frequency of daytime urinary incontinence episodes at baseline and week 6, including change from baseline. The treatment difference in mean change from baseline for 200 versus 50 U BOTOX and 100 versus 50 U BOTOX will be calculated. Pairwise comparisons of 200 versus 50 U BOTOX and 100 versus 50 U BOTOX at week 6, will be evaluated using an analysis of covariance (ANCOVA) model; a hierarchical analysis strategy to adjust for multiplicity will be used. A similar analysis, without a hierarchical testing strategy, will be applied to other timepoints and to the secondary efficacy variables (pairwise comparisons will be done up to week 12).

A preliminary estimate of duration of effect will be evaluated as time from treatment on day 1 to request for retreatment using a Kaplan-Meier survival analysis. Dose-response analyses will include a nonparametric area under the curve (AUC) analysis of daily average frequency of daytime urinary incontinence episodes.

The health outcomes parameters of PinQ and Modified TBS will be analyzed using either an analysis of variance (ANOVA) or ANCOVA for continuous variables, or using Pearson's chi-square test, Fisher's exact test (or CMH) for categorical variables as appropriate on the mITT population.

[figure not shown]
For safety variables, data from all patients who received study drug will be included; data will be analyzed using the dose actually received, with all patients allocated to the nearest dose group (50, 100, or 200 U BOTOX).

**Sample Size Calculation:** The sample size calculation for this study is determined empirically. A total of 34 patients per treatment group are to be randomized for the study (30 patients per treatment group plus additional patients to address patient attrition [estimated to be 10% by week 6]).

[figure not shown]
The following table displays the estimated distance for treatment differences between 200 U BOTOX (maximum 6 U/kg) and 50 U BOTOX (maximum 6 U/kg) in mean daily average frequency of daytime episodes of urinary incontinence change from baseline at week 6 for a range of common standard deviations (SD). All calculations assume 30 patients per treatment group and a 2-sided test significance level of 0.05. The calculation was performed using the commercial software nQuery Advisor (procedure MTC0-1), version 6.01, and the confidence interval is based on the large sample z statistic.

Standard Deviation	Distance From Mean to the Limit
2.0	1.012
2.5	1.265
3.0	1.518
3.5	1.771
4.0	2.024

Note: The ranges of the SDs are determined based on the values from the adult pivotal phase 3 studies (191622-515 and 191622-516). The estimate of the SD for the 200 U BOTOX treatment group is 3.44 for Study 191622-515, 2.58 for Study 191622-516, and 3.10 for the 2 studies combined.

## 1 Background and Clinical Rationale

### *Neurogenic Detrusor Overactivity in Pediatric Patients*

The urinary bladder has 2 principal functions, to adequately store urine (storage phase), and to efficiently empty urine (voiding phase). Coordination of these functions is accomplished through a complex interaction between the peripheral innervations of the lower urinary tract and the micturition centers of the central nervous system (CNS).

Attainment of voluntary bladder control occurs once the appropriate coordinated neurological development has occurred, which usually starts from approximately 2 to 3 years of age. However, if there is a spinal cord lesion, an interruption of the spinal pathways and higher CNS micturition centers that control bladder function occurs. In children, this is most commonly due to incomplete neural tube closure during embryonic development, with traumatic or neoplastic lesions of the spinal cord being less common. The most common form of incomplete neural tube closure is spina bifida, where some vertebrae overlying the spinal cord are not fully formed and remain unfused and open. Myelomeningocele is the most commonly presenting form of spina bifida in which there is a protrusion of both the meninges that cover the spinal cord and the spinal cord itself through the unfused vertebrae; the meningeal membranes usually form a sac enclosing the spinal elements. In meningocele, an uncommon form of spina bifida, the vertebrae have developed more normally; however, the meninges have been forced into the gaps of the vertebrae. In the mildest form, spina bifida occulta, the gap in the vertebrae is so small that there is no protrusion of spinal cord or meninges and it often remains undetected. To avoid further nerve damage and infection in spina bifida patients, early surgical intervention usually occurs in order to put any protruding spinal cord and its nerve roots back inside the spine, which is then covered with meninges. This can lead to a subsequent complication during growth, where the scar tissue at the site of the meningocele closure causes a tethering of the spinal cord.

A tethered cord can also occur through congenital malformations such as presence of a spur of bony tissue in the spinal canal (split cord syndrome), growth of fatty tissue at the base of the developing spinal cord that entangles it (lipomeningomyelocele), an incomplete involution of the distal spinal cord leading to a thickened filum terminale (tight filum terminale syndrome), or it may be due to an injury in later life. However, the shared common feature is that the spinal cord is attached to the spinal column rather than hanging free in the canal. Since the spinal cord grows more slowly than the spinal column, a tethered spinal cord becomes stretched and stressed over time, causing neurological damage in the cord.

Less commonly in the pediatric population, a spinal cord lesion can be caused by a direct spinal insult/injury, or be due to a demyelination of the nerves (transverse myelitis); the latter may have various potential causes (eg, viral infection, immune disorder).

Regardless of the source of the spinal cord lesion, it commonly results in a neurogenic bladder, which often exhibits detrusor overactivity; since there is a known neurological cause this is termed neurogenic detrusor overactivity (NDO). Detrusor overactivity is defined as an involuntary detrusor contraction (IDC) during filling cystometry ([Abrams et al, 2002](#)), so this mainly affects the storage phase of the bladder. At bladder fill volumes which would normally be accommodated by the bladder, detrusor muscle contractions occur through efferent neuronal activity via the spinal micturition centers to the detrusor muscle. This abnormal efferent activity may be a consequence of the abnormal neuronal input to the detrusor, as well as a malfunction of the afferent signals from the bladder. Essentially, the bladder has an inability to appropriately store urine resulting in uninhibited detrusor contractions that frequently result in uncontrolled urinary incontinence.

In addition to urinary incontinence, patients with NDO frequently suffer from a low capacity bladder and high intravesical pressures with uncoordinated bladder sphincter activity ([Van Gool et al, 2001](#)). This can put at risk the upper urinary tract due to vesico-ureteric reflux, particularly when uncontrolled bladder contractions occur against a closed bladder outlet. This has been clearly demonstrated in pediatric patients ([McGuire et al, 1981](#); [Bauer et al, 1984](#); [Gerridzen et al, 1992](#)).

